2. STUDY OBJECTIVES AND ENDPOINTS

Primary Objective (Safety):	Primary Endpoints (Safety):
 To evaluate the safety profile of 13vPnC in infants and children 7 months to <6 years of age (Cohorts 2, 3, and 4) as measured by the incidence rates of local reactions, systemic events (including the use of antipyretic medication, and adverse events (AEs). 	 The incidence of local reactions and systemic events (including the use of antipyretic medication) in the 7 days after each vaccination (13vPnC or Hib) in Cohorts 2, 3 and 4. The incidence of AEs from the signing of the informed consent document (ICD) to 1 month after the last vaccination (13vPnC or Hib) in Cohort 2, 3 and 4. The incidence of newly diagnosed chronic medical conditions from 1 month after the last study vaccination (13vPnC or Hib) to 6 months after the last study vaccination in Cohort 2, 3 and 4. The incidence of serious adverse events (SAEs) from the signing of the informed consent document (ICD) to 6 months after the last study vaccination (13vPnC or Hib) in Cohort 2, 3 and 4.
Secondary Objectives (Immunogenicity):	Secondary Endpoints (Immunogenicity):
• To describe the functional antibody responses as measured by opsonophagocytic activity (OPA) to the 13 pneumococcal serotypes induced by 13vPnC in infants and children 7 months to <6 years of age (Cohorts 2, 3, and 4) compared to responses in infants 6 weeks to 2 months of age (Cohort 1).	• The serotype-specific OPA geometric mean titers (GMTs) for each of the pneumococcal serotypes measured in a subset of approximately 50 subjects per cohort measured 1 month after the last dose of 13vPnC in Cohort 2, 3, 4 compared to OPA GMTs measured 1 month after the infant series in Cohort 1.
• To describe the immune responses to 13vPnC compared to Hib vaccinated controls in Cohorts 2, 3, and 4.	 Serotype specific IgG GMC in all subjects and OPA GMTs in approximately 50 subjects per cohort vaccinated with 13vPnC (Cohorts 1,2,3 4) and approximately 25 subjects per cohorts vaccinated with Hib (Cohort 2, 3, 4) using blood drawn at the following visits: Cohort 2: Visit 1, Visit 4 Cohort 3: Visit 1, Visit 3 Cohort 4: Visit 1, Visit 2
• To describe the circulating antibody levels to the 13 pneumococcal serotypes from before vaccination through 5 years of age (4 years after the last study vaccination) in Cohort 1.	• Serotype specific IgG GMC in all subjects and OPA GMTs in approximately 50 subjects at all times points in Cohort 1.

Secondary Objective (Safety):	Secondary Endpoints (Safety):	
• To evaluate the safety profile of 13vPnC as measured by the incidence rates of adverse events (AEs) in Cohort 1.	 The incidence of AEs from the signing of the informed consent document (ICD) to 1 month after vaccination 3 in Cohort 1. The incidence of newly diagnosed chronic medical conditions from 1 month after vaccination 3 to vaccination 4 in Cohort 1. The incidence of AEs from vaccination 4 to 1 month after vaccination 4 in Cohort 1. The incidence of newly diagnosed chronic medical conditions from 1 month after vaccination 4 in Cohort 1. The incidence of newly diagnosed chronic medical conditions from 1 month after vaccination 4 to 6 months after vaccination 4 in Cohort 1. The incidence of serious adverse events (SAEs) from the signing of the informed consent document (ICD) to 6 months after vaccination 4 in Cohort 1. 	

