Axillary temperature	Х	Х	Х		Х			
Assign subject number in the interactive	Х							
response technology (IRT) or equivalent								
system								
Obtain blood sample	Х			Х	Х	Х		Х
Vaccination and 30-minute observation	13vPnC	13vPnC	13vPnC		13vPnC			
Confirm continued eligibility		Х	Х	Х	Х	Х	Х	Х
Adverse event collection as appropriate	Х	Х	Х	Х	Х	Х	Х	Х
for visit								

Table 1.	Study Flowchart for	Cohort 1 (2 Months	[42 to 56 Days of Age a	t Consent])
----------	---------------------	---------------------------	-------------------------	-------------

a. Persistence blood draw visits will take place when the subject is 2 years, 3 years, 4 years and 5 years of age. The permitted visit windows are Visit 8: 2 Years of age to 2 years and 28 days of age; Visit 9: 3 years of age to 3 years and 28 days of age; Visit 10: 4 years of age to 4 years and 28 days of age; Visit 11: 5 years of age to 5 years and 28 days of age.

Table 2. Study I low chart for Condit 2 (7 months [210 Days] to minimum of fige at Consent
--

Visit Number	1	2	3	4	5
Visit Description	Vaccination	Vaccination	Vaccination	Post-Toddler	6-Month
	1	2	3	Dose visit	Follow-up Telephone Contect
Visit Window	210 to <365 Days of Age	At Least 28 Days After Visit 1	365 Days to <450 Days of Age and at Least 56 Days After Visit 2 ^a	28 to 42 Days After Visit 3	168 to 196 Days After Last Study Vaccination
Informed consent	Х				
Review inclusion/exclusion criteria	Х				
Demography, medical history, and physical examination	Х				
Record nonstudy vaccines	X	Х	Х	Х	Х
Axillary temperature	X	Х	X ^b		
Randomization in the interactive response technology (IRT) or equivalent system	X				
Obtain blood sample	X			Х	
Vaccination and 30-minute observation; investigational product as randomized ^e	13vPnC or Hib vaccine	13vPnC or Hib vaccine	13vPnC ^d		
Confirm continued eligibility		Х	Х	Х	
Provide parent with diary, thermometer, and measuring device, if necessary	Х	Х	X ^b		
Assess reactogenicity and the use of antipyretic medication	Days 1 to 7	Days 1 to 7	Days 1 to 7 ^b		
Review diary data			Х		
Collect the diary			X ^e	X ^b	
Adverse event collection as appropriate for visit	X	Х	Х	Х	Х

a. The third dose must be given at age 12 months to less than 15 months of age and at least 56 days after the second vaccination.

b. 13vPnC recipients only.

c. Subjects will receive 13vPnC or active comparator (*Haemophilus influenzae* type b vaccine [Hib vaccine]) according to age-appropriate schedules.

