- Based on clinical evaluation, determine whether any AEs (including SAEs) have occurred since the last study visit and record them on the CRF.
- Record any nonstudy vaccinations.
- Ensure that the subject continues to be eligible for the study; refer to Subject Withdrawal section of the protocol.
- Collect the e-diary (Hib recipients only).
- Subjects randomized to Hib vaccine will not receive a vaccination at Visit 3. Subjects randomized to Hib may receive a third dose of Hib vaccine according to local practice or national recommendations, at the discretion of the investigator. Investigational sites will be reimbursed for any Hib vaccinations given. Hib vaccinations will be given outside of the study.

13vPnC recipients only:

- On the day of vaccination, measure and record the subject's axillary temperature.
- Ensure the subject does not meet any of the temporary delay criteria.
- Administer a single 0.5-mL intramuscular injection of 13vPnC into subject's left limb (left anterolateral thigh muscle or deltoid of the left arm) in accordance with the local package insert.
- Observe the subject for at least 30 minutes after vaccination for any significant acute reactions. Any AE noted during the observation period should be recorded in the source documents and in the AE section of the CRF.
- Issue a measuring device and a digital thermometer (if necessary) to the caregiver and provide instructions on their use.
- Issue a subject e-diary (if necessary) to the caregiver and provide instruction on its completion.
- Ask the caregiver to contact the investigator or other site staff immediately if any significant illness or hospitalization occurs during the study period, or if the subject reports redness or swelling at the investigational product injection site measuring >14 units on the measuring device.
- Remind the caregiver to bring the e-diary to the next study visit.
- Ask the caregiver to contact the investigator or other site staff immediately if any significant illness or hospitalization occurs during the study period.
- Schedule an appointment with the caregiver for the next study visit.

- The investigator or an authorized designee completes the CRF and updates the investigational product accountability records.
- The e-diary data should be viewed online via the vendor portal at frequent intervals from Day 1 to Day 7 after vaccination to evaluate e-diary completion and compliance and as part of the ongoing safety review.

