8.1.4. Time Period for Collecting AE/SAE Information

The time period for actively eliciting and collecting AEs and SAEs ("active collection period") for subjects in Cohort 1, begins from the time the subject's /parent(s)/legal guardian provides informed consent, which is obtained before the subject's participation in the study (ie, before undergoing any study-related procedure and/or receiving investigational product), through and including Visit 4 and from Visit 5 to Visit 6. Between Visits 4 and 5 and between Visits 6 and 7, only SAEs and newly diagnosed chronic medical conditions will be

recorded. The subject's parent/legal guardian will be asked to report any AEs that occur within 48 hours after the blood draw at Visits 8, 9, 10, and 11.

The time period for actively eliciting and collecting AEs and SAEs ("active collection period") for subjects in Cohort 2, 3, and 4, begins from the time the subject's /parent(s)/legal guardian provides informed consent, which is obtained before the subject's participation in the study (ie, before undergoing any study-related procedure and/or receiving investigational product) until 1 month after the last vaccination (13vPnC or Hib). At the 6-Month follow-up telephone contact (final telephone contact), the parent(s)/legal guardian will be contacted to inquire about SAEs, including hospitalizations and newly diagnosed chronic medical conditions since the previous visit.

For subjects who are screen failures, the active collection period ends when screen failure status is determined.

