6.4.1. Adverse Events

It should be recognized that most studies are not designed to reliably demonstrate a causal relationship between the use of a pharmaceutical product and an AE or a group of AEs. Except for select events in unique situations, studies do not employ formal adjudication procedures for the purpose of event classification.

For tier 1 and tier 2 events, the proportion of AEs observed in each vaccine group will be presented along with the point estimates and associated 95% CIs of the risk difference (the difference of incidence rates) between 13vPnC and Hib vaccine in Cohort 2, 3, 4.

For tier 1 events, 95% CIs will be calculated using the exact methods proposed by Chan and Zhang described in Section 5.2.1.

For tier 2 events, 95% CIs will be calculated using the Miettinen and Nurminen method described in Section 5.2.1.

For tier 1 events, p-values from Chan and Zhang's method will be calculated and included in the presentations. AEs will be arranged in the output sorted in descending order of point estimates of the risk difference (the difference of incidence rates) within system organ class.

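### In Cohorts 2 and 3 the adverse-event window for 13vPnC recipients runs through the whole gap before their last dose, so the 13vPnC-versus-Hib risk differences are hard to interpret whichever way Hib time is counted

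*Protocol*

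**What the plan says.** Protocol section 2 (repeated in SAP 3.1.2) gives Cohorts 2 to 4 a single AE window: "The incidence of AEs from the signing of the informed consent document (ICD) to 1 month after the last vaccination (13vPnC or Hib". The chronic-condition endpoint takes over where that window ends: "newly diagnosed chronic medical conditions from 1 month after the last study vaccination (13vPnC or Hib) to 6 months after the last study vaccination". Protocol 8.1.4 ends active AE collection in these cohorts at the same point, 1 month after the last dose of whichever vaccine was given.

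The last dose differs by arm. In Cohort 2, 13vPnC recipients get dose 3 at "365 Days to <450 Days of Age and at Least 56 Days After Visit 2", while Hib recipients get no study vaccination at that visit. In Cohort 3, 13vPnC recipients get a second dose at least 56 days after the first, with no stated upper limit, and Hib recipients get none.

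The visit procedures do not follow that split. At Cohort 2 Visits 3 and 4 (Protocol 6.2.3 and 6.2.4), sites must "determine whether any AEs (including SAEs) have occurred since the last study visit and record them on the CRF", with no restriction to one arm. Cohort 3 Visits 2 and 3 read the same way.

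Cohort 1 handles its long gap before the toddler dose differently. The endpoint there is "The incidence of newly diagnosed chronic medical conditions from 1 month after vaccination 3 to vaccination 4 in Cohort 1", and Protocol 8.1.4 matches it: "Between Visits 4 and 5 and between Visits 6 and 7, only SAEs and newly diagnosed chronic medical conditions will be" recorded.

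SAP 6.4 asks for safety summaries by dose but does not say when a dose's period ends. SAP 6.4.1 compares the arms: "For tier 1 and tier 2 events, the proportion of AEs observed in each vaccine group will be presented", together with 13vPnC-minus-Hib risk differences and confidence intervals, and p-values for tier 1.

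**The concern.** An endpoint that counts a child once for any event in a window depends on how long the window is and how much of it lies near a dose. For Cohort 2 13vPnC recipients most of the window can be ordinary infant life, months from any injection. AEs from the gap are also elicited at one visit, covering up to 211 days.

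AE incidence is a primary safety measure for the age expansion, and the Hib arm is there as the safety control. If the risk differences mainly reflect observation time or background illness, they say little about the vaccine. The bias can go either way, depending on which text the programmer follows.

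**Working it through.** **Check on the windows.** The only figure in the documents built on these windows is Cohort 2 participation, up to about 14 months (Protocol 3.2). Entry at day 210, dose 3 at day 449 and the last contact 196 days later give (449 − 210) + 196 = 435 days, or 435 / 30.44 = 14.3 months. It reproduces.

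**Cohort 2 intervals.** Inputs: Visit 1 at 210 to 364 days of age; Visit 2 at least 28 days later; Visit 3 at 365 to 449 days of age and at least 56 days after Visit 2; Visit 4 at 28 to 42 days after Visit 3.
- Dose 2 to dose 3: shortest 56 days; longest 449 − (210 + 28) = 211 days.
- Visit 1 to Visit 4: shortest 28 + 56 + 28 = 112 days; longest (449 − 210) + 42 = 281 days.
- Days more than 30 from any dose: (56 − 30) = 26 of 112 (23%) at the short end; (211 − 30) + (42 − 30) = 193 of 281 (69%) at the long end.

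**Reading A: each arm closes 1 month after its own last dose.** I take 1 month as 28 to 42 days, matching the follow-up visit window, and dose 2 at day 28. 13vPnC is then observed 112 to 281 days and Hib 28 + 28 = 56 to 28 + 42 = 70 days. The ratio runs from 126 / 70 = 1.8 to 267 / 56 = 4.8. In Cohort 3, 13vPnC has at least 56 + 28 = 84 days against 28 for Hib, or 98 against 42.

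Assume the same AE rate in both arms and no vaccine effect, with P = 1 − exp(−rate × days / 30) and a 28-day closing visit:

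| Rate per 30 days | Gap 56 days: 13vPnC v Hib | Gap 211 days: 13vPnC v Hib |
|---|---|---|
| 0.05 | 17.0% v 8.9% | 35.9% v 8.9% |
| 0.1 | 31.2% v 17.0% | 58.9% v 17.0% |
| 0.2 | 52.6% v 31.2% | 83.1% v 31.2% |
| 0.3 | 67.4% v 42.9% | 93.1% v 42.9% |

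The spurious difference is 8 to 52 points, against 13vPnC.

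**Reading B: both arms counted to Visit 4.** Assume background risk b per 30 days and 5% added by each of three 13vPnC doses. Then P(13vPnC) = 1 − (1 − b)^(days/30) × 0.95³ and P(Hib) = 1 − (1 − b)^(days/30). The z values use 118 v 59 children and an unpooled standard error.
- b = 10%, 281 days: 68.0% v 62.7%, difference 5.3 points, z = 0.70.
- b = 10%, three 30-day windows: 37.5% v 27.1%, difference 10.4 points, z = 1.42.
- b = 10%, 112 days: z = 1.27, so little is lost.
- b = 5%: z is 1.13 over 281 days and 2.00 over three 30-day windows. b = 20%: 0.34 and 0.92.

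**The two readings side by side.** With b = 10% and the same added risk, the longest windows under reading A (281 v 70 days) give 68.0% v 21.8%, a difference of 46 points. Reading B gives 5.3 points for the same children.

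**The case against.** A reader might infer that the gap is AE time for the whole of Cohort 2, so that the harm is simply dilution. The documents do not support that. Hib recipients have no dose at Visit 3. By the endpoint wording and Protocol 8.1.4 their AE window closes 1 month after Visit 2, and their later time is already chronic-condition time. Dilution arises only under the visit procedures.

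A reader might also infer that Cohort 2 reverses the Cohort 1 rule and loses chronic conditions. That goes too far. Cohort 1 also has one continuous AE window across doses 1 to 3 (42 + 42 + 28 = 112 to 70 + 70 + 42 = 182 days from dose 1), and its chronic-condition endpoint omits that period too. Its switch comes at a scheduled visit, which Cohort 2 lacks between doses 2 and 3. In 13vPnC recipients, chronic conditions arising in the gap still count as AEs, and as SAEs if serious.

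Other objections stand in part:
- SAP 5.1 and 6.1.2.1 make the primary safety analysis descriptive, by group. The between-arm differences are nevertheless planned in SAP 6.4.1.
- Tier 2 is defined by preferred term, so individual rates will be lower than the any-AE rates used here. Lower rates reduce dilution, but under reading A the ratio of proportions then approaches the ratio of the windows.
- Solicited reactions already have 7-day windows. Unsolicited AEs do not.
- The 281-day case is an extreme, and giving Hib no AE effect is a simplification.
- Cohort 3 participation of about 8 months fits Visit 2 near day 56 (56 + 196 = 252 days, 8.3 months), but this is an expectation and not a limit.

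**Conclusion.** The point holds in this form: for 13vPnC recipients in Cohorts 2 and 3 the AE window runs unbroken through the gap before the last dose, no per-dose limit is set, and the texts disagree on when Hib observation ends. The endpoint wording gives a spurious 13vPnC excess. The visit procedures give a difference pulled towards zero.

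The intervals (56 to 211 days; 112 to 281 days) follow from the visit windows. The risks do not: the documents give no AE rates, so all percentages and z values rest on assumed rates. Dilution is small when the gap is short. The excess under reading A is 8 to 25 points even at a 56-day gap over the rates tried.

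A reader might conclude that the primary endpoint must be redefined. That is not needed, and it would require a protocol amendment if major (Protocol section 9, SAP section 2). An added analysis is enough.

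**What to change.** 1. Reconcile the endpoint wording (Protocol section 2, SAP 3.1.2), Protocol 8.1.4 and the Cohort 2 and 3 visit procedures, so that the end of AE counting in the Hib arm is stated once.
2. In SAP 6.4.1 keep the full-period table. Add, for Cohorts 2 and 3, AE proportions and tier 1 and 2 risk differences restricted to onset within 1 month after each scheduled dosing visit. Use the same visits in both arms, including the one where Hib recipients get no study dose, and note non-study Hib doses given around it. This removes the distortion under either reading.
3. Optionally, add a supporting row for newly diagnosed chronic conditions from the first dose to the 6-month contact. That contact is timed from each arm's own last dose. With dose 2 at day 28, it falls 28 + 168 = 196 to 28 + 196 = 224 days after dose 1 for Hib, and can fall as late as day 435 for 13vPnC. Show follow-up days by arm beside it.

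The cost is one extra table and, for item 3, a medical flag for chronic conditions among recorded AEs. No new data are needed if sites followed the visit procedures in both arms. That should be confirmed, because the Hib window after the no-dose visit lies outside active collection under Protocol 8.1.4. SAP section 2 says the primary-report analyses have already been run, so the added table should be labelled supportive and post hoc.

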3. STUDY DESIGN

3.1. Description

- This is a phase 3 randomized, open-label study to evaluate the safety, tolerability, and immunogenicity of 13vPnC of infants and young children who are naïve to pneumococcal vaccination.
- Subjects will be stratified into 4 cohorts defined by their age at consent:
 - Cohort 1: Subjects 6 weeks (42 days) to 2 months (56 days) of age;
 - Cohort 2: Subjects 7 months (210 days) to <12 months (<365 days) of age;
 - Cohort 3: Subjects ≥ 1 year to ≤ 2 years of age;
 - Cohort 4: Subjects ≥ 2 years to < 6 years of age.
- Subjects in Cohort 1 will all receive 13vPnC at 2, 4, 6 and 12 to 15 months of age. See Table 5 below.
- Subjects in Cohorts 2, 3, and 4 will be randomized into 2 groups in a 2:1 ratio to receive 13vPnC or comparator (Hib vaccine) according to age-appropriate schedules. See Table 5 below.

		Age at first vaccination	Age at second vaccination	Age at third vaccination	Age at fourth vaccination
Cohort 1	13vPnC	42 to 56	42 to 70 Days	42 to 70 Days	365 to 455
		Days of Age	After Visit 1	After Visit 2	Days
					of Age
Cohort 2	13vPnC	7 to <12	At Least 28 Days	365 Days to <450 Days	
	or	Months of Age	After Visit 1	of Age and at Least 56	
_	Hib			Days After Visit 2 ^a	
Cohort 3	13vPnC	≥ 1 to ≤ 2	At Least 56 Days		
	or	Years of Age	After Visit 1 ^b		
	Hib				
Cohort 4	13vPnC	≥ 2 to ≤ 6		_	
	or	Years of Age			
	Hib	_			

Table 5.Age at Vaccination

a. Subjects in Cohort 2 randomized to Hib vaccine will not receive a vaccination at Visit 3. These subjects may receive a third dose of Hib vaccine according to local practice or national recommendations, at the discretion of the investigator.

b. Subjects in Cohort 3 randomized to Hib vaccine will not receive a vaccination at Visit 2.

3.2. Approximate Duration of Subject Participation

Subjects in Cohort 1 are expected to participate from the first vaccination to the final visit which will include an antibody persistence blood draw 4 years after the last 13vPnC vaccination.

Subjects in Cohorts 2, 3 and 4 are expected to participate from the first vaccination to the final phone call, which will be the 6 months after the last vaccination.

The total duration of subject participation is up to approximately:

- Subjects in Cohort 1 will participate for up to approximately 5 years
- Subjects in Cohort 2 will participate for up to approximately 14 months
- Subjects in Cohort 3 will participate for approximately 8 months
- Subjects in Cohort 4 will participate for approximately 6 months

3.3. Approximate Duration of the Study

This study is anticipated to last approximately 66 months, assuming a 6-month recruitment period. The total duration may differ depending on the actual enrollment rate. Enrollment into the 4 cohorts will take place simultaneously. The end of the study is the last visit of the last subject in Cohort 1, which is scheduled approximately 48 months after the last vaccination.

3.4. Approximate Number of Subjects

Approximately 656 Chinese subjects will be randomized in four different age cohorts (Cohorts 1, 2, 3, and 4 with N=125, 177, 177, and 177 respectively).

An additional 280 subjects (177 subjects of Cohort 2, 73 subjects of Cohort 3, and 30 subjects of Cohort 4) will be enrolled from county CDCs.

There will be at least 1 coordinating center which may coordinate the study activities of multiple enrolling sites. Randomized subjects who withdraw from the study may be replaced to maintain adequate numbers to achieve study objectives.

4. SUBJECT ELIGIBILITY CRITERIA

This study can fulfill its objectives only if appropriate subjects are enrolled. The following eligibility criteria are designed to select subjects for whom participation in the study is considered appropriate. All relevant medical and nonmedical conditions should be taken into consideration when deciding whether a particular subject is suitable for this protocol.

Subject eligibility should be reviewed and documented by an appropriate member of the investigator's study team before subjects are included in the study.

